## 6 INTRODUCTION

### 6.1 Background

Amyotrophic lateral sclerosis (ALS) is a rare disease that causes progressive and fatal neurodegenerative disorders. Currently, incurable, respiratory failure leads to death in a mean time of 2 to 4 years for the majority of ALS subjects, after the onset of the first symptoms. However, 5–10% of subjects may survive for a decade or more.

Early stages of the disease appear in several forms and the lack of biological markers make ALS particularly difficult to diagnose. ALS is typically diagnosed by excluding other possible diseases. The El Escorial criteria have been developed and revised by the World Federation of Neurology; the criteria are based on clinical signs, electrophysiological and neuroimaging evidence, and allow for the diagnosis of ALS in 5 categories: definite ALS, probable ALS, probable laboratory-supported ALS, possible ALS, or suspected ALS.

ALS is a disease of unknown cause in which primary motor neurons (upper motor neurons) and secondary motor neurons (lower motor neurons) degenerate and are lost selectively and progressively. The symptoms are dominated by muscle atrophy and muscle weakness, with upper limb dysfunction, gait disturbance, dysarthria, dysphagia, and respiratory impairment appearing with the progression of illness, and with no sensory dysfunction or dysuria. As the mechanism of motor neuron death, excitatory amino acid hypothesis, free radical hypothesis, and viral infection hypothesis have been proposed.

Rilutek® (Riluzole) was first approved by the United States (US) Food and Drug Administration (FDA) in December 1995. Riluzole is indicated to extend life or the time to mechanical ventilation for subjects with ALS and represents the baseline standard of pharmacological care. Additional care is provided to reduce symptomatic medical concerns. Survival of ALS subjects has improved over time, mainly as a result of the improvement in the symptomatic care of ALS.

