7.2. Statistical Tests

This study is a long-term, open-label safety study. As a result, no formal hypothesis testing is planned for this study. The long-term safety and tolerability of oral edaravone will be evaluated in exploratory manner using descriptive statistics. For exploratory efficacy analysis, point estimates and their associated 95% Confidence Interval will be presented.

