8.4.1.2.2. ALS History²:**Continuous:**

- (1) Disease duration from onset of symptoms to Screening and from ALS diagnosis to A01 Screening (year),
- (2) ALSFRS-R score at A01 Screening

Categorical:

- (3) Disease duration from onset of symptoms to A01 Screening and from ALS diagnosis to A01 Screening categorized at <1 year vs \geq 1 year,
- (4) Initial symptom categorized as 'Bulbar symptom' or 'Limb symptom',
- (5) ALS Diagnosis categorized 'Sporadic' or 'Familial',
- (6) Categorical El Escorial revised Diagnostic,
- (7) Concomitant use of riluzole 'Present' or 'Absent'
(Note: The concomitant riluzole used after the first dose of Study A01 will be included),
- (8) Previous exposure to edaravone before Study A01 'Yes' or 'No'

If the ALS diagnosis date is incomplete, it will be imputed as follows:

- If the ALS diagnosis date is completely missing, the subjects will not be included for the calculation.
- If the start day and month are missing, then the first day of the first month (January) will be used.

Table 4: ALS History Parameters

| Category | Item | Type of Data | Definition/Breakdown |
|---------------------|---|--------------|--|
| ALS Disease History | Disease duration from onset of symptoms to A01 screening (year) | Continuous | (Date of Screening - Date of Onset of Symptoms)/365.25 |
| | | Binary | < 1 year, \geq 1 year |
| | Disease duration from ALS diagnosis to A01 screening (year) | Continuous | (Date of Screening - Date of Diagnosis)/365.25 |
| | | Binary | < 1 year, \geq 1 year |
| | ALSFRS-R score at A01 screening | Continuous | |

² ALS history will be taken from MT-1186-A01

Statistical Analysis Plan
Protocol No. MT-1186-A03

Mitsubishi Tanabe Pharma America, Inc.

| | | | |
|--|--|-------------|--|
| | Initial symptom | Binary | Bulbar symptom, Limb symptom |
| | ALS diagnosis | Binary | Sporadic, Familial |
| | El Escorial revised Airlie House Diagnostic Criteria | Categorized | Clinically Definite ALS, Clinically Probable ALS, Clinically Probable laboratory-supported ALS, or Clinically Possible ALS |
| | Concomitant use of riluzole | Binary | Present, Absent |
| | Previous exposure to edaravone before Study A01 | Binary | Yes, No |

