9.2.1. Efficacy Endpoints

For the efficacy endpoints, continuous data will be summarized at each analysis visit using summary statistics. Absolute values and changes from baseline will be presented. All categorical endpoints will be summarized at each analysis visit, using frequency tabulations. As the primary purpose of this study is to explore the safety of edaravone and not to perform confirmatory analyses, there will be no formal hypothesis testing performed and adjustments for multiplicity are not required.

9.2.1.1. ALSFRS-R change from baseline up to Week 96

The ALSFRS-R score of each item, domain score and total score will be listed. The total ALSFRS-R score and change from baseline to each post baseline visit up to week 96 will be plotted by visit. This analysis will be made on the safety analysis population.

The changes from baseline to (CHG) all post-baseline visits until week 96 in ALSFRS-R will be estimated using a Mixed Model for Repeated Measures (MMRM). The model includes response data from all post-baseline visits with no imputation for missing data. The ALSFRS-R at baseline (BASE), concomitant riluzole (RI) and visit (AVISIT) at week 24, 48, 72 and 96 will be included as fixed factors in the model. An unstructured covariance structure will be assumed and the denominator degrees of freedom will be computed using the Kenward-Roger method. In case the model will not converge with the unstructured covariance structure, the heterogeneous Toeplitz structure (TOEPH), Heterogeneous Autoregressive(1) (ARH(1)) , the heterogeneous compound symmetry (CSH), Toeplitz (TOEP), First-order autoregressive (AR(1)), and Compound symmetry (CS) will be used instead (in that order). The changes from baseline and their associated 95% Confidence Limits will be estimated, separately for each visit, from the same MMRM using LSMEANS estimates.

The SAS code planned for the analysis is outlined below.

[REDACTED]

For subgroup analysis, the above MMRM model will be employed using the corresponding subgroup categorical variable and the interaction between the subgroup and visit.

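### Unless the redacted SAS code sets other weights, the ALSFRS-R visit means give riluzole users and non-users equal weight and so do not estimate the treated cohort's mean change

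*SAP*

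**What the plan says.** The model for change in ALSFRS-R is in SAP 9.2.1.1: "The ALSFRS-R at baseline (BASE), concomitant riluzole (RI) and visit (AVISIT) at week 24, 48, 72 and 96 will be included as fixed factors". There is no riluzole-by-visit term. Each visit's estimate and interval come from that model: "The changes from baseline and their associated 95% Confidence Limits will be estimated, separately for each visit, from the same MMRM using LSMEANS estimates". SAP 8.4.1.2.2 makes riluzole a two-level variable ("Concomitant use of riluzole 'Present' or 'Absent"). The text then announces the program ("The SAS code planned for the analysis is outlined below"), but the code is redacted in the public copy. For region, the same model is refitted with region and its interaction with visit added.

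Three other places matter:
- Protocol 17.3.5.1 planned descriptive statistics with a 95% CI at each visit in the safety set, without a model.
- SAP 9.2.1 keeps observed means and changes by visit, but the summary statistics defined in SAP 7.1 include no CI. SAP 7.2 says only in general terms that "point estimates and their associated 95% Confidence Interval will be presented". The LSMEANS interval is therefore the only ALSFRS-R interval whose calculation is specified.
- Protocol 6.1 says of riluzole that it "represents the baseline standard of pharmacological care".

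**The concern.** With one treated group there is no contrast in which covariate weights would cancel. Whatever weights LSMEANS put on riluzole go straight into the published mean. By default, LSMEANS weight the levels of a class factor equally, whatever the real split. If riluzole is standard care, non-users are probably the smaller group, yet they would carry half the weight.

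The default also sets the baseline covariate at its mean over analysis records, so subjects who stay longer count more often.

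Readers will take the figure as the mean change of the treated subjects, which is what the protocol planned to estimate. Under default weights it would describe a notional population with half its members on riluzole. Region means would inherit the same weighting, with fewer non-users in each region.

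**Working it through.** The documents give no SD, riluzole share, riluzole effect or interval width, so there is no planned figure to reproduce.

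**Inputs from the documents:** N about 140 (SAP 4.2); visits at Weeks 24, 48, 72 and 96; fixed effects baseline, riluzole and visit; 95% intervals, two-sided per the protocol (z = 1.96).

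**Assumed inputs:** p from 0.5 to 0.9; b in points; SD of change 4/6/8/9 at the four visits; correlation falling with distance between visits, 0.6 to 0.9 between neighbours; 90/75/60/50% observed, with the same dropout in users and non-users; equal mean baseline in both groups; known covariance.

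**Step 1. Shift.** Let m1 and m0 be the mean changes of users and non-users, with b = m1 - m0.

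Equal weights minus cohort weights = (0.5m1 + 0.5m0) - (p·m1 + (1 - p)m0) = (0.5 - p)b.

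This gives 0 at p = 0.5, -0.2b at 0.7, -0.3b at 0.8 and -0.4b at 0.9. The model has one riluzole effect for all visits, so the shift is the same at every visit. A larger sample does not remove it.

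**Step 2. Standard error at a single visit.** The ratio of equal to cohort weights is 1/sqrt(4p(1 - p)): 1.09 at p = 0.7, 1.25 at 0.8, 1.40 at 0.85 and 1.67 at 0.9.

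**Step 3. Standard error in the planned MMRM.** Step 2 is not the planned model. For the MMRM, V is the inverse of the sum over subjects of X'C⁻¹X, and SE = sqrt(L'VL). L has 1 for the visit and either 0.5 or p for riluzole. With correlation 0.8, the entries are SE with equal weights / SE with cohort weights (ratio):

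| p | Week 24 | Week 48 | Week 72 | Week 96 |
|---|---|---|---|---|
| 0.5 | 0.36/0.36 (1.00) | 0.55/0.55 (1.00) | 0.79/0.79 (1.00) | 0.96/0.96 (1.00) |
| 0.7 | 0.39/0.36 (1.09) | 0.57/0.55 (1.04) | 0.80/0.79 (1.02) | 0.97/0.96 (1.01) |
| 0.8 | 0.44/0.36 (1.24) | 0.61/0.55 (1.11) | 0.83/0.79 (1.05) | 1.00/0.96 (1.04) |
| 0.9 | 0.58/0.36 (1.62) | 0.72/0.55 (1.29) | 0.91/0.79 (1.15) | 1.06/0.96 (1.11) |

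Over correlations 0.6 to 0.9, the widening at p = 0.8 is 20 to 25% at Week 24 and 3 to 4% at Week 96. At p = 0.9 it is 54 to 63% and 10 to 11%. It shrinks with time because the single riluzole effect is estimated mostly from the early, less variable visits.

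As half-widths at p = 0.8: Week 24, 1.96 × 0.44 = 0.86 against 1.96 × 0.36 = 0.71 points; Week 96, 1.96 × 1.00 = 1.96 against 1.96 × 0.96 = 1.88 points.

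**Step 4. Coverage of the cohort mean.** At p = 0.8 and b = 2 the shift is 0.3 × 2 = 0.6 points in size. At Week 24, 0.6/0.44 = 1.36 standard errors, so coverage is Φ(1.96 + 1.36) - Φ(-1.96 + 1.36), about 72%. The four visits give about 72, 83, 89 and 91%. With b = 0, coverage is 95% throughout.

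**The case against.** The strongest objection is that the redacted block would show exactly what is in dispute. Observed margins, or riluzole coded 0/1 as a covariate, would remove the equal weighting. The wording does not settle it either: the same sentence calls baseline, a continuous score, a fixed factor, so that term does not prove riluzole is a class variable. This stands. A reader might infer from the text that equal weighting is established; the documents do not show that, and the point has to be conditional.

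A reader might also apply the single-visit formula and conclude that the interval is 40% too wide at p = 0.85. The planned model does not support that as a flat figure. On the assumptions above, the p = 0.85 ratio is about 1.3 to 1.4 at Week 24 and 1.05 to 1.06 at Week 96. That fall depends on the SD growing over time: with an SD of 9 at every visit, the Week 96 ratio would be 1.18 to 1.30, still below 1.40.

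Nor is too wide the right description of the fault. The interval is correct for the 50:50 mean. For the cohort mean, the problem when b is not 0 is that it is centred in the wrong place.

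Three further points limit the stakes:
- A small non-user group is an inference from one background sentence; the trial only permits riluzole.
- The observed mean change is still reported, and a CI could be worked out from its n and SD.
- The endpoint is exploratory and "no formal hypothesis testing is planned for this study".

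These lower the severity. They do not make an equally weighted LSMEANS interval describe the treated cohort.

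**Conclusion.** The point holds conditionally and is of low severity. The SAP text leaves the riluzole weighting of the visit means unstated. If the code uses riluzole as a class factor with default LSMEANS, the reported mean is for a 50:50 mix and lies (0.5 - p)b from the cohort mean, so its interval is off-centre whenever p is not 0.5 and b is not 0. The larger standard error is the secondary effect: marked at Week 24 and small by Week 96 if SDs grow as assumed.

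All sizes rest on assumed p, b, SDs, correlations and dropout. There is no shift if p = 0.5 or b = 0, and no widening if p = 0.5. No test or decision depends on this interval. The case for acting is that the remedy is almost free and makes the estimate match the population readers will assume.

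**What to change.** In SAP 9.2.1.1, state that the visit LSMEANS use observed riluzole margins taken from a dataset with one record per safety-population subject (the OM=dataset option), with baseline ALSFRS-R fixed at the subject-level mean of that population. Margins taken over visit records would over-weight subjects who stay longer.

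In the region model, use each region's own riluzole margins and baseline mean. Imposing the pooled riluzole mix on every region would leave each region's mean not describing its own subjects.

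If the redacted code already does this, say so in the text.

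The cost is a sentence or two in the SAP and the matching LSMEANS options. No new data are needed. With cohort weights the shift is removed and, at p = 0.8 with correlation 0.8, the standard errors move from 0.44/0.61/0.83/1.00 to 0.36/0.55/0.79/0.96 under the stated assumptions.

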9.2.1.2. Time to death, tracheostomy, or permanent assisted mechanical ventilation

The following parameter will be listed, plotted using Kaplan Meier methods and summarized by Kaplan-Meier methods with 95% confidence interval, the number of events and percentage. This analysis will be made on FAS.

- The time to first onset (TIMETO) of death, tracheostomy or permanent assisted mechanical ventilation from first study drug administration in the MT-1186-A01 study.

In supportive analysis, the time to death, time to permanent assisted mechanical ventilation and time to tracheostomy will be analyzed separately using Kaplan-Meier methods.

The SAS code planned for the analysis is outlined below.

[REDACTED]
[REDACTED]
[REDACTED]

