## **9.6 Withdrawal of Individual Subjects**

A subject will be withdrawn from the study if the subject meets any of the following criteria:

- Requests to be withdrawn from the study;
- Has been found to be ineligible for participation in the study;
- The investigator (or subinvestigator) concludes that a subject should be withdrawn if continuation in the study is difficult due to AEs (e.g., hypersensitivity reactions);
- Is pregnant;
- Requires tracheostomy;
- Requires permanent assisted mechanical ventilation ( $\geq 23$  hours/day);
- The investigator (or subinvestigator) judges' continuation of the study to be inappropriate due to exacerbation of the primary disease;
- Development of significant liver dysfunction:
  - ALT or AST greater than 8 times the ULN;
  - Persistent ALT or AST of greater than 5 times the ULN for at least 2 weeks;
  - ALT or AST greater than 3 times the ULN AND elevated total bilirubin greater than 2 times ULN;
  - Symptoms consistent with liver dysfunction (e.g., fatigue, nausea, vomiting, abdominal pain/tenderness, fever, rash, eosinophilia  $>5\%$ ) with concomitant ALT or AST greater than 3 times the ULN.
- Note: Subjects meeting these criteria do not require withdrawal if alternative etiology is identified on discussion with the Study Medical Monitor.
- Noncompliance (i.e., misses more than 20% of doses in 2 consecutive dosing cycles, after consultation with MTDA or designee).

If a subject is withdrawn prematurely from the study, the date the subject is withdrawn from the study and the reason for withdrawal will be recorded in the electronic case report form (eCRF).

In the event that a subject drops out of the study at any time, the reason for discontinuation must be fully documented in the source documents and the eCRF. The Investigator site personnel will document the AEs and any other assessments in the source documents and will make every effort to complete all required early termination (ET) assessments. Study sites must make all efforts to follow-up with phone calls.

Subjects who are withdrawn from the study following enrollment may not re-enter the study.

The study may be terminated by the Sponsor at any time upon becoming aware of data that could compromise the safety and/or well-being of subjects or for any other reason it deems appropriate.

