4. STUDY DESIGN

4.1. Study Design

[figure not shown]
This is a Phase 3, international, multi-center, open-label, long-term extension study following the MT-1186-A01 study. The study will evaluate the safety of edaravone at a dose of 105 mg administered once daily for 10 days out of 14, followed by a 14-day drug-free period up to 96 weeks of treatment or until the drug is commercially available in that country.

Subjects who complete treatment in Study MT-1186-A01 and meet eligibility criteria will be enrolled into this open-label treatment study (MT-1186-A03) and will continue to receive 105 mg of edaravone once daily following an overnight fast, and subjects must continue to fast at least 1 to 2 hours before the next meal (e.g., breakfast). Treatment cycles will occur every 28 days (10 days on study drug out of a 14-day period, followed by 14 days off study drug).

Concomitant use of riluzole will be permitted during the study. Subjects who discontinue from the study before Week 96 will complete the procedures listed in Week 96 within 7 days of discontinuation as End of Study (EOS) procedures.

Further details can be found in the Study Schema (Figure 1: Study Schema). The schedules of assessment for each country specific (Germany and France) are referred to each country specific protocol.

Figure 1: Study Schema

Abbreviation: ET = early termination; EOT = end-of-treatment; EOS = end-of-study.

a. Subjects will receive oral edaravone at a dose of 105 mg administered once daily for 10 days out of a 14-day period, followed by a 14-day drug-free period. The dose of edaravone should be taken following an overnight fast and at least 1 to 2 hours before the morning meal.

b. Day 1 is equal to the Week 48 visit of the MT-1186-A01 study.

Table 1: Schedule of Activities for Global

| Assessment | Week (window) | Open-label Treatment Period | | | | | | Safety Follow-up Period ^a |
|--|---------------|---|--------------|--------------|--------------|--------------|------------------------------------|--------------------------------------|
| | | Day 1 (Based upon Week 48 procedures from 1186-A01) | 12 (± 7D) | 24 (± 7D) | 36 (± 7D) | 48 (± 7D) | 60 Telephone Visit (± 7D) | |
| Cycle | 1 | 4 | 7 | 10 | 13 | 16 | 19 | 24 |
| Visit | 1 | 2 | 3 | 4 | 5 | 6 | 7 | 9 |
| Informed consent | X | | | | | | | |
| Eligibility criteria | X | | | | | | | |
| Demographics ^b | X | | | | | | | |
| Vital signs ^c | X | X | X | X | X | X | X | X |

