8.4.2.1. ALSFRS-R Total score

ALSFRS-R is a questionnaire used to measure the impact of ALS that is evaluated by the Investigator. The scale measures the subjects' physical function across 12 activities of daily living. The date of the evaluation along with the results will be recorded on the eCRF with respect to "4 Handwriting" and "5 eating motion," the results for the dominant hand (the hand used in daily life at the time of screening) will be recorded.

- ALSFRS-R total score will be derived from the sum of 12 items⁴. For the item 5 "Eating disorder," either the item (a) or (b) will be selected corresponding to subjects without or with gastrostomy respectively. The maximum total core is $4 \times 12 = 48$. If there is missing score data in an item, ALSFRS-R total score will be missing.
- ALSFRS-R domains Score
 - Bulbar function = total of items 1 to 3
 - Limb function = total of items 4 to 9
 - Fine motor function = total of items 4 to 6
 - Gross motor function = total of items 7 to 9
 - Respiratory function = total of items 10 to 12

If there is missing score data in an item, the corresponding domain score will be missing.

8.4.2.2. Time to death, tracheostomy, or permanent assisted mechanical ventilation:

The time to first occurrence of death, tracheostomy, or permanent assisted mechanical ventilation (defined on EMA Guideline on clinical investigation of medicinal products for the treatment of amyotrophic lateral sclerosis, 1 November 2015) will be derived as follow:

- In case the event mentioned above is observed any time from MT-1186-A01 first date of study drug, up to the last observed visit date, then the time variable for each subject will be calculated as:
 - The date of the event - First date of study drug in MT-1186-A01 +1
- In case the event mentioned above is **not** observed any time up to the last observed visit date, a right censoring will be performed for each subject at the last observed date regardless of treatment status. the time variable for each subject will be calculated as:
 - Last observed Date - First date of study drug in MT-1186-A01 +1

⁴ Refer to Appendix I of the protocol.

- Indicator (censoring) variable will be created to indicate an event (0) if the event was observed or censoring (1) if the event was not observed and at week 96 database lock the subjects was either discontinued or completed.

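### The supportive tracheostomy and permanent-ventilation analyses use Kaplan-Meier with no visible rule for death; cumulative incidence with death competing would give the proportion affected

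*SAP*

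**What the plan says.** The main time-to-event variable is the first of death, tracheostomy or permanent assisted ventilation, counted from the first study drug dose in MT-1186-A01 and analysed on the full analysis set. SAP 9.2.1.2 has it "summarized by Kaplan-Meier methods with 95% confidence interval, the number of events and percentage". The same section then adds, as supportive work, that "the time to death, time to permanent assisted mechanical ventilation and time to tracheostomy will be analyzed separately using Kaplan-Meier methods". Planned SAS code follows, but it is redacted.

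The only visible derivation is in SAP 8.4.2.2, and it is written for the composite. Its event bullet begins "In case the event mentioned above is observed any time from MT-1186-A01 first date of study drug, up to the last observed visit date". For subjects without an event, "a right censoring will be performed for each subject at the last observed date regardless of treatment status". The coding line reads "Indicator (censoring) variable will be created to indicate an event (0) if the event was observed", with 1 for censoring. There is no third state. Protocol 17.3.5.2 also describes only the composite.

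Two further passages bear on this. Protocol 9.6 lists "Requires tracheostomy" and "Requires permanent assisted mechanical ventilation" among the reasons for withdrawal, and asks sites to keep following subjects by telephone. Protocol 13.2 schedules calls at Weeks 24, 48, 72 and 94 after study drug is stopped, to find out whether any of the three events has occurred.

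**The concern.** In the composite, death is an event, so no competing-risk question arises. In a curve for tracheostomy alone, or for permanent ventilation alone, a subject who dies first can no longer have the event. If that death is censored like a loss to follow-up, Kaplan-Meier treats the subject as still able to have the event later. One minus the curve then estimates a probability in a hypothetical setting without death, not the share of subjects who go on to tracheostomy or ventilation.

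The two curves may well be looked for. Protocol 7.2.2 and 13.2 list the three times as separate items, whereas the protocol synopsis and SAP 3.2.2 list the composite. The number and percentage of events are promised for the composite; the supportive sentence promises only Kaplan-Meier. At stake is the reading of two descriptive curves.

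**Working it through.** **Inputs from the documents.** Maximum follow-up from the first MT-1186-A01 dose is 48 + 96 = 144 weeks, or 144 × 7 / 365.25 = 2.76 years. Protocol 6.1 and SAP 1 put death at a mean of 2 to 4 years after first symptoms for most patients. About 140 subjects are expected in this study; the size of the full analysis set is not given. No rate of death, tracheostomy or ventilation is stated, so there is no figure of the plan's own to reproduce.

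**Assumptions.** Constant, independent hazards. Let *a* be the cumulative hazard of the component event over follow-up and *d* that of death. A death hazard *d* corresponds to mortality 1 − exp(−*d*) if nothing else occurred.

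**Formulas.**
- Kaplan-Meier with deaths censored: 1 − KM = 1 − exp(−*a*).
- Cumulative incidence with death competing: CIF = *a*/(*a*+*d*) × [1 − exp(−(*a*+*d*))].

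**Result for *a* = 0.1**, where 1 − KM = 1 − exp(−0.1) = 9.52% throughout:

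| *d* | Mortality | CIF | Excess of 1 − KM (points) |
|---|---|---|---|
| 0.105 | 10% | 9.04% | 0.48 |
| 0.3 | 25.9% | 8.24% | 1.27 |
| 0.5 | 39.3% | 7.52% | 2.00 |
| 0.7 | 50.3% | 6.88% | 2.63 |
| 1.0 | 63.2% | 6.06% | 3.45 |
| 1.4 | 75.3% | 5.18% | 4.34 |

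Example, *d* = 0.3: 0.1/0.4 × (1 − exp(−0.4)) = 0.25 × 0.3297 = 8.24%. A simulation of 400,000 subjects gave 8.27% at *d* = 0.3 and 5.22% at *d* = 1.4, in line with the formula.

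**Other component hazards, *d* from 0.3 to 1.4.**
- *a* = 0.05: 4.88% against 4.22% to 2.64%, an excess of 0.66 to 2.24 points.
- *a* = 0.2: 18.13% against 15.74% to 9.98%, an excess of 2.39 to 8.15 points.

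**A milder grid.** With mortality of 10% to 50% and a 1 − KM value of 5% to 20%, the excess runs from about 0.3 to 5.4 points. In simulated samples of 140 with 40% mortality and a 10% event probability, 1 − KM averaged 10.1% and cumulative incidence 7.9%.

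**Is the death range plausible?** A constant hazard with a mean of 2 to 4 years gives 2.76/2 = 1.38 to 2.76/4 = 0.69 over 144 weeks, inside the range shown. This is rough context only, because those means run from symptom onset and not from the first MT-1186-A01 dose.

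**The other non-fatal event.** If it also competes, with the same hazard *a*, then CIF = *a*/(2*a*+*d*) × [1 − exp(−(2*a*+*d*))]. At *a* = 0.1 this is 7.87% (*d* = 0.3) to 4.99% (*d* = 1.4), which is 0.37 to 0.19 points below the table. At these hazards the choice matters less than death, but it changes the figure and should be stated.

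**The case against.** The strongest reply is the redaction. The code stands directly after the sentence at issue and may settle how death is coded, so the plan cannot be called silent. That stands: only the visible text lacks a rule. But the visible text does fix the method as Kaplan-Meier, and the only visible coding has two states.

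Second, Kaplan-Meier with deaths censored is a recognised cause-specific summary, not a calculation error. It misleads only if read as the proportion affected, and the SAP nowhere says it will be reported that way. This also stands, and it limits the point to a cheap improvement.

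Third, the excess can be smaller than the sampling error. If 140 subjects were fully followed, a 9.5% estimate would have a 95% half-width of 1.96 × √(0.095 × 0.905/140) = 4.9 points, more than any excess in the table. True, but the excess is systematic, always upward, and avoidable using the same dates.

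Some stronger readings are tempting, and the documents do not support them:
- *Withdrawal at one non-fatal event ends follow-up for the other.* Largely answered by the telephone follow-up in Protocol 9.6 and 13.2 and by SAP 8.4.2.2, which censors irrespective of treatment status. What stays open is whether the other event formally competes.
- *The event bullet in SAP 8.4.2.2 excludes deaths after the last visit.* The words allow it, but it would remove most deaths from an endpoint that includes death. The indicator line carries no visit limit, and SAP Table 1 labels a contact "60 Telephone Visit", so a visit need not be in clinic.
- *MT-1186-A01 discontinuers in the full analysis set go unfollowed.* Their follow-up would be described in the MT-1186-A01 protocol, which is not among these documents.
- *The three separate curves contradict the composite because they do not add up to it.* That comparison requires the death curve to be censored at non-fatal events, which no visible text states, and the SAP never adds the curves.

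**Conclusion.** The point holds as a modest improvement to two supportive curves. If deaths are censored, as the visible two-state coding suggests but does not prove, the curves overstate the proportion of subjects reaching tracheostomy or permanent ventilation. The size depends wholly on assumed constant, independent hazards, with the low end of the table at 10% mortality and the high end at 75%. If the redacted code already treats death as competing, only the SAP wording needs to change.

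The endpoint is exploratory, the study has one arm, and SAP 7.2 plans no hypothesis test. The date terms in SAP 8.4.2.2 are a wording matter, to which no size is attached.

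**What to change.** In SAP 9.2.1.2:
- For time to tracheostomy and time to permanent ventilation, replace Kaplan-Meier with Aalen-Johansen cumulative incidence and its 95% confidence interval, with death as a competing event.
- State whether the other non-fatal event also competes, or whether follow-up continues past it through the telephone contacts in Protocol 9.6 and 13.2.
- Keep Kaplan-Meier for the composite and for time to death.

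In SAP 8.4.2.2, as a wording alignment only: define one last-known-status date that includes telephone contacts and death dates. Use it in the event bullet, the censoring bullet and the indicator line, in place of the two undefined date terms.

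The cost is a few sentences and minor programming. The event and death dates are those already needed for the planned analyses, so no new data collection is required. If deaths were going to be censored, the two reported figures will come out somewhat lower.
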